#### 4.2 Population Characteristics

Treatment-naïve advanced or metastatic renal cell carcinoma patients in Germany or Austria will be included in this study: males and females aged 18 years and older, with the intention to be treated with cabozantinib or cabozantinib-nivolumab combination according to the current local SmPCs taken prior to the entry in the study.

#### 4.3 Data Collection

Data from subjects suffering from advanced or metastatic renal cell carcinoma and treated first line with cabozantinib or cabozantinib-nivolumab combination will be collected.

Subjects will be treated in accordance with current local SmPCs during their participation in this study. No additional assessment or test will be required.

Relevant data collected as part of routine medical care will be captured in an eCRF. These data will be transmitted to the data management vendor managed by the sponsor for analysis. The data transmitted will be pseudonymised and will be identified by a numeric identifier.

All the collected data will be in accordance with the daily practice of medical doctors dedicated to treatment of subjects suffering from advanced or metastatic renal cell carcinoma. If some data is not collected, he/she will mark the corresponding sections in the eCRF as not done.

#### 4.4 Study Duration

The study will be considered to have started when the first subject has signed informed consent (first subject in).

The study will be considered to be completed after the last subject has had its last visit (LSV).

Planned duration:

- First subject in (FSI): Q3 2018
- Last subject in (LSI): Q2 2025
- Time for recruitment: approx. 7years
- Last subject last visit (LSLV): Q2 2027
- Final clinical study report (CSR): Q2 2028
- Total study duration: 10 years
- Subject participation duration: 2 years

#### 4.5 Subject Information

Prior to enrolment of a subject in this study, the investigator, or a person designated by the investigator, will explain the nature and purpose of this data collection to each subject, or each subject's legally acceptable representative. As all assessments and procedures will be conducted in accordance with routine medical practice, participation in the study does not convey any additional risks or burdens for the subject. However, the subject will be required to provide written informed consent to confirm that they allow their medical data to be collected and analysed. For data privacy reasons, the subject must give his consent that his contact data will be given out to the vendor (German Sportsuniversity Cologne) who is in charge of the handling of questionnaires and actigraphs.

This must be obtained prior to subject enrolment and prior to any data being entered in the study database. Sufficient time should be allowed to discuss any questions raised by the subject. The subject should be allowed as much time as they need to consider their decision.

The sponsor will provide an informed consent form, in German language readily understood by the subject. Each subject's original consent form personally signed and dated by the subject or

by the subject's legally acceptable representative, and by the physician, who conducted the informed consent discussion, will be retained by the investigator. The investigator will supply all enrolled subjects with a copy of their signed informed consent. None of these informed consents will be collected by the sponsor.

The consent form will be revised during the study if important new information becomes available.

## 5 STUDY POPULATION

Eligible subjects for this study are systemic treatment-naïve adult subjects with advanced or metastatic renal cell carcinoma, scheduled to be treated with cabozantinib or Cabozantinib-nivolumab combination prior to entry in the study. Currently 35 subjects are treated with cabozantinib in monotherapy. It is planned to include 175 subjects treated with cabozantinib-nivolumab combination.

It is planned to recruit up to 50 sites in Germany and Austria, both practices and hospitals.

### 5.1 Inclusion Criteria

All subjects must fulfil the following:

- (1) Males or females aged 18 years and older with capacity to consent.
- (2a) Subjects receiving cabozantinib or cabozantinib-nivolumab combination as a first line treatment for advanced or metastatic renal cell carcinoma.
- (3a) Subjects with the intention to be treated with cabozantinib or cabozantinib-nivolumab combination according to the current SmPC; decision has to be taken before entry in the study.
- (4) Signed written informed consent.

### 5.2 Exclusion Criteria

Subjects will not be included in the study if the following apply:

- (1) Participation in an interventional study at the same time and/or within 3 months before baseline.
- (2) Previous participation in this study.

### 5.3 Subject Withdrawal Criteria

As this is a non-interventional study, no specific withdrawal criteria are specified. Subjects are free to withdraw consent at any time. Data will be collected up to the time of withdrawal, but no additional information will be collected after this time.

When a subject is withdrawn from the study, the primary reason should be recorded in the eCRF. The reason can be adverse event, withdrawal by subject or guardian, lost to follow-up, protocol deviation, physician decision, site terminated by sponsor, study terminated by sponsor, pregnancy, death or other.

## **6 STUDY ASSESSMENTS**

Study Flow Chart [Table 2](#) shows the data that can be recorded in the eCRF at each of these visits.

Table 2 Flowchart

Visit	Visit 1 Baseline	Visit 2	Visit 3	Visit 4	Visit 5	Visit 6	Visit 7	Visit 8	Visit 9	Visit 10	Follow-up (FU) 1	FU 2
Assessment / Procedure	Day 1	4	8	12	16	24	32	40	48	56	30 days after TD	1 year after TD or 24 months after V1
Signature of informed consent	✓	informed consent must be signed prior to any documentation of data										
Visit date	✓	✓	✓	✓	✓	✓	✓	✓	✓	✓	✓	✓
Eligibility	✓											
Demographics (gender, year of birth)	✓											
Significant Medical or Surgical History	✓											
Disease history	✓											
Prior nephrectomies	✓											
Overall response		✓	✓	✓	✓	✓	✓	✓	✓	✓		
ECOG Performance Status	✓	✓	✓	✓	✓	✓	✓	✓	✓	✓		
Cabozantinib / cabozantinib-nivolumab regimen	✓	✓	✓	✓	✓	✓	✓	✓	✓	✓		✓*
Vital signs	✓	✓	✓	✓	✓	✓	✓	✓	✓	✓		
Inflammatory markers	✓			✓		✓		✓		✓		
Occupational status and smoking status	✓			✓		✓		✓		✓		
Quality of life questionnaire°	✓			✓		✓		✓		✓		
Activity questionnaire°	✓			✓		✓		✓		✓		
Actigraph measurement (1 week) °†	✓			✓		✓		✓		✓		
Adverse Events		✓	✓	✓	✓	✓	✓	✓	✓	✓	✓	✓
Concomitant medication for AEs		✓	✓	✓	✓	✓	✓	✓	✓	✓	✓	✓
Study discontinuation or completion form		✓	✓	✓	✓	✓	✓	✓	✓	✓	✓	✓
Post cabozantinib / cabozantinib-nivolumab systemic treatment for RCC											✓	✓

All data will be recorded as applicable and available: if a specific diagnostic procedure is done according to clinical routine the corresponding data should be recorded in the eCRF, otherwise the corresponding part of the eCRF will be marked as not done. TD: Treatment discontinuation, \*: only for subjects who have performed visit 10, °: not collected in eCRF, collected from patient by German Sport University Cologne; † only in centres where activity measurement is part of clinical routine

## 6.1 Study Assessments

All data will be recorded as applicable and available. In other words, if a specific diagnostic procedure is done according to clinical routine, the corresponding data should be recorded in the eCRF, otherwise the corresponding part of the eCRF will be marked as not done.

The timing of the visits according to routine clinical practice is assumed to be close to the proposed schedule. If the timing does not meet the schedule, entries should be made at the visit nearest in time to the proposed schedule.

The following data will be collected at the following visits:

### Visit 1, baseline (enrolment):

- Date of informed consent signature
- Visit date
- Eligibility (verification of in- and exclusion criteria)
- Demographics (gender, year of birth)
- Significant Medical or Surgical History
- Disease history (date of renal cell carcinoma diagnosis, RCC stage at diagnosis, RCC stage at baseline (TNM), cancer histology, risk score either by IMDC or MSKCC)
- Prior Nephrectomies (occurrence and date)
- ECOG Performance Status
- Smoking status and Occupational status
- Vital Signs (Height and body weight, blood pressure)
- Inflammatory blood markers (hsCRP or CRP, as available, no safety marker)
- Quality of life questionnaire (NFKSI-19) after Visit 1 (within 2 weeks)
- Activity questionnaire after Visit 1 (within 2 weeks)
- Actigraph measurement (1 week) after Visit 1 (within 2 weeks) [only in centres where activity measurement is part of clinical routine]

### Visits 2/3/5/7/9 - (about 4, 8, 16, 32 and 48 weeks, respectively, after baseline)

- Visit date
- Evaluation of tumour (Overall response)
- ECOG Performance Status
- Vital Signs (Body weight, blood pressure)
- Adverse Events
- Concomitant medication for AEs
- Cabozantinib regimen (Start date, stop date, dose, frequency, time of day of intake, primary reason for dose change or discontinuation)
- Nivolumab regimen (dose and date of injection, reason for injection delayed if any and primary reason for nivolumab discontinuation)
- Study discontinuation or completion form (in case of discontinuation: reason for premature withdrawal)

### Visits 4/6/8/10 - (about 12, 24, 40 and 56 weeks, respectively, after baseline):

- Visit date

- Evaluation of tumour (Overall response)
- ECOG Performance Status
- Adverse Events
- Concomitant medication for AEs
- Cabozantinib regimen (Start date, stop date, dose, frequency, time of day of intake, primary reason for dose change or discontinuation).
- Nivolumab regimen (dose and date of injection, reason for injection delayed if any and primary reason for nivolumab discontinuation)
- Smoking status and Occupational status
- Vital Signs (Body weight, blood pressure)
- Inflammatory blood markers (hsCRP or CRP, as available, no safety marker)
- Quality of life questionnaire (NFKSI-19) after the visit
- Activity questionnaire after the visit
- Actigraph measurement (1 week) after the visit [only in centres where activity measurement is part of clinical routine]
- Study discontinuation or completion form (in case of discontinuation: reason for premature withdrawal)

Follow-up visit (FU) 1 - (about 30 days after treatment discontinuation):

- Visit date
- Adverse Events
- Concomitant medication for AEs
- Post Cabozantinib / cabozantinib-nivolumab combination systemic treatment for RCC
- Study discontinuation or completion form (in case of discontinuation: reason for premature withdrawal)

Follow-up visit (FU) 2 - (1 year after treatment discontinuation or 24 months after visit 1):

- Visit date
- Adverse Events
- Concomitant medication for AEs
- Post Cabozantinib /cabozantinib-nivolumab combination systemic treatment for RCC
- Cabozantinib regimen (dose and date for last cabozantinib intake; only for patients who continued until visit 10)
- Cabozantinib-nivolumab combination regimen (dose and date for last cabozantinib and nivolumab intake; only for patients who continued until visit 10)
- Study discontinuation or completion form (in case of discontinuation: reason for premature withdrawal)

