Study Timelines	
Expected median duration of cabozantinib treatment is approx. 8-9 months, expected median duration of cabozantinib-nivolumab treatment is approximately. 14 months, for 1st line treatment (IV). Study duration including a 2-year follow-up was from Q3 2018 – Q2 2026 and will be extended. This extension includes a 1-year-enrollment phase (Q2 2024 – Q2 2025) and 2-year follow-up (Q2 2025 - Q2 2027).

Study Design:	
Prospective German and Austrian multicenter non-interventional study (NIS) with approximately 50 centers in Germany and Austria.

Study Population:	
Inclusion Criteria
 
(1) Males or females aged 18 years and older with capacity to consent.
 
(2a) Subjects receiving cabozantinib or cabozantinib-nivolumab combination as a first line treatment for advanced or metastatic renal cell carcinoma.
 
(3a) Subjects with the intention to be treated with cabozantinib or cabozantinib-nivolumab combination according to the current SmPC; decision has to be taken before entry in the study.
 
(4) Signed written informed consent.
 
Exclusion Criteria
 
(1) Participation in an interventional study at the same time and/or within 3 months before baseline.
 
(2) Previous participation in this study.

Study Treatment:	
In this non-interventional study, cabozantinib or cabozantinib-nivolumab combination are to be administered as directed by the investigator according to the current SmPCs and the study site’s usual clinical practice. The physician should refer to the SmPCs of the study medications for any information on the treatment prescribed.

Study Evaluations:	
 
- Treatment characteristics: starting dose, dose reductions, dose interruptions, dose delay, treatment discontinuation;
 
- Demographic and baseline characteristics: medical history and baseline characteristics of RCC and demographics;
 

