### 4.1 Overview

This is an international, multicentre, non-interventional prospective study. Data will be collected via electronic case report form (eCRF) by the sites.

This study will be conducted in Germany and Austria, which have a cabozantinib tablets Marketing Authorisation (MA) for first line use. MA for the cabozantinib-nivolumab combination as first line treatment in advanced or metastatic RCC was in March 2021. Patients intended to be treated with this combination can be enrolled as soon as the MA is in place for use of these products in the European Union.

Investigators will follow their individual therapeutic concept for the treatment with cabozantinib or cabozantinib-nivolumab combination in accordance with the current SmPC.

No out-of-routine diagnostic or therapeutic intervention is allowed during this study. All data recorded in this study originate from routine diagnostic and therapeutic procedures.

The investigator needs to inform the subject that personal and medical data will be recorded for this study. The subject has to give written informed consent for data collection, data processing and for monitoring purposes.

Data will be collected at the described visits:

- Visit 1 (baseline): enrolment visit,
- Visit 2 (approximately 4 weeks after baseline),
- Visit 3 (approximately 8 weeks after baseline),
- Visit 4 (approximately 12 weeks after baseline),
- Visit 5 (approximately 16 weeks after baseline),
- Visit 6 (approximately 24 weeks after baseline),
- Visit 7 (approximately 32 weeks after baseline),
- Visit 8 (approximately 40 weeks after baseline),
- Visit 9 (approximately 48 weeks after baseline),
- Visit 10 (approximately 56 weeks after baseline),
- Follow-up 1 (30 days after treatment discontinuation),
- Follow-up 2 (1 year after treatment discontinuation or 24 months after baseline if subjects reached visit 10).

The timing of the visits according to routine clinical practice is assumed to be close to the proposed schedule. If the timing does not meet the schedule, entries should be made at the visit nearest in time to the proposed schedule.

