If a subject discontinues the intake of cabozantinib or of cabozantinib-nivolumab combination at any visit before Visit 10, the follow-up period starts, and the next visit will be Follow-up 1. Discontinuation of the cabozantinib-nivolumab combination is defined as the permanent discontinuation of both study medications. i.e. as soon as one of the treatments is still ongoing the combination is not considered as discontinued. The Follow-up period can only start once both treatments have been permanently discontinued.

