#### **7.1.1 Primary Endpoints & Evaluations**

The primary endpoints are to describe the use of cabozantinib /cabozantinib-nivolumab combination in terms of:

- number and proportion of subjects with dose reduction of cabozantinib due to SAEs/AEs,
- number and proportion of subjects with dose interruption of cabozantinib and/or nivolumab due to SAEs/AEs,
- number and proportion of subjects with termination of cabozantinib /cabozantinib-nivolumab combination due to SAEs/AEs,
- injection delayed of nivolumab due to SAE/AE,

in subjects with advanced or metastatic renal cell carcinoma (mRCC) treated in real-life clinical setting in 1st line treatment overall and split by risk score

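### The primary endpoints have no time limit, but dose changes and stops are recorded with reasons only to week 56, so later AE-related first events can go unrecorded

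*Protocol*

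**What the plan says.** **Endpoint.** Protocol 7.1.1 lists the primary endpoints, for example "number and proportion of subjects with dose reduction of cabozantinib due to SAEs/AEs", with matching entries for interruption, termination and delayed nivolumab injection. Section 9.4.4.1 analyses the share of subjects with an AE-related event of each type, with a 95% confidence interval, overall and by risk group. Neither section sets a time window.

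**Collection to week 56.** At Visits 2 to 10, section 6.1 takes "Cabozantinib regimen (Start date, stop date, dose, frequency, time of day of intake, primary reason for dose change or discontinuation". For nivolumab it takes injection dates and doses, the reason for any delay, and the primary reason for discontinuation. The last of these visits is "Visit 10 (approximately 56 weeks after baseline".

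**Collection after week 56.** Section 4.1 schedules "Follow-up 2 (1 year after treatment discontinuation or 24 months after baseline if subjects reached visit 10". At that visit, section 6.1 and the Table 2 footnote limit the regimen entry to subjects who reached Visit 10. The combination entry is "Cabozantinib-nivolumab combination regimen (dose and date for last cabozantinib and nivolumab intake; only for patients who continued until visit 10"; the monotherapy entry is its counterpart for cabozantinib. Follow-up 1 has no regimen entry.

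**Expected exposure.** The synopsis gives "expected median duration of cabozantinib-nivolumab treatment is approximately. 14 months" and, for monotherapy, "Expected median duration of cabozantinib treatment is approx. 8-9 months".

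**The concern.** A subject still on treatment at week 56 whose first AE-related reduction, interruption or injection delay comes later has no regimen field in which it can be entered. If the subject stops, the date of last intake is known at Follow-up 2, but not whether an AE was the reason. Unless another source supplies the link, the subject counts as a non-event in a proportion that 7.1.1 and 9.4.4.1 present as covering first-line treatment as a whole.

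The shortfall would grow with time on treatment. It would differ between the two cohorts, and between risk groups if their treatment durations differ. Section 9.4.3 is also affected: it plans primary reasons for discontinuing study treatment for the full analysis set, and these are not collected for stops after Visit 10. An analysis plan cannot restore reasons that were never collected.

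**Working it through.** **Plan's own precision (9.3), 167 combination subjects.** Half-width = 1.96 × √(p(1−p)/167).
- p = 0.15: 5.42% (stated 5.4%).
- p = 0.55: 7.55% (stated 7.5%).

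Both reproduce.

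**Where week 56 falls.** 56 × 7 / 30.4375 = 12.88 months. The expected combination median is 14 months, or 14 × 30.4375 / 7 = 60.9 weeks. Because 12.88 < 14, at least half of the combination cohort is expected to be on treatment at Visit 10 under any duration curve with that median. This takes treatment as starting at about baseline; it holds as long as treatment starts no more than 14 − 12.88 = 1.1 months earlier.

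**Share still on treatment at week 56.** The protocol gives no distribution, so the shape is assumed: S(t) = 0.5^((t/median)^k), where k = 1 is exponential.

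| Cohort | Median (months) | k | Share | Subjects |
|---|---|---|---|---|
| Combination | 14 | 1 | 52.9% | 88 of 167 |
| Combination | 14 | 0.7 to 2 | 52.0% to 55.6% | 87 to 93 of 167 |
| Monotherapy | 8 to 9 | 1 | 32.8% to 37.1% | 11 to 13 of 35 |

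These shares are subjects at risk of an unrecorded event, not subjects who lose one.

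**Illustration, AE-related termination (combination).** Assume constant hazards, a constant AE share of stops, and 15% as the eventual rate. S(12.88) = 0.5285 and S(24) = 0.5^(24/14) = 0.3048.
- By week 56: 0.15 × (1 − 0.5285) = 7.07 points, reason recorded.
- Week 56 to month 24: 0.15 × (0.5285 − 0.3048) = 3.36 points, date recorded but no reason.
- After month 24: 0.15 × 0.3048 = 4.57 points, beyond Follow-up 2.

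The last two sum to 7.93 points. If all AE-related terminations come before week 56, the loss is 0. The range is therefore 0 to about 8 points.

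**Illustration, first cabozantinib reduction.** Assume constant hazards and 55% ever reduced. Stopping hazard d = ln 2 / 14 = 0.0495 per month; reduction hazard a = d × 0.55/0.45 = 0.0605; sum 0.1100.
- By week 56: 0.55 × (1 − e^(−0.1100 × 12.88)) = 41.7 points.
- Later: 55 − 41.7 = 13.3 points, about 22 of 167 subjects.

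This too shrinks towards 0 if first reductions come early.

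**Could another form supply the missing link?**
- *AE pages.* Table 2 and 6.1 list AEs at Follow-up 1 and 2, but 7.2 ends safety collection at Follow-up 1.
- *Follow-up 1.* The explicit trigger in 4.1 concerns stops "at any visit before Visit 10, the follow-up period starts, and the next visit will be Follow-up 1". Whether it is held after a later stop is not stated.
- *Study discontinuation form.* It asks for the reason for premature withdrawal, which 5.3 ties to leaving the study. A subject can stop treatment for an AE and stay in the study.
- *Minimum AE report (10.2.3).* It does not include the action taken with the drug.

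**The case against.** **The AE pathway may close part of the gap.** AEs and their concomitant medication are listed at both follow-up visits. Section 9.4.6 plans tables of treatment-emergent AEs leading to cabozantinib interruption, reduction or discontinuation, and of those associated with nivolumab delay, interruption or discontinuation. That requires AEs to be linked to dose actions somewhere, and the full AE form is not shown. This stands as far as it goes: some later events may be recoverable. But no section names the AE form as the source for the primary endpoint, and the sections disagree on whether AE collection reaches Follow-up 2.

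**A reader might infer that primary-endpoint data stop at week 56 and that events are lost for over half of all subjects.** The documents do not support that. Follow-up 2 captures the date and dose of last intake. The endpoints count subjects with at least one event, so anyone with a first event by week 56 is already counted. The share above one half applies to the combination cohort only.

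**A reader might also infer a bias of 8 points, larger than the 5.4% precision.** That figure is the upper end under assumed constant hazards. It reads a rate reported in another trial as an eventual rate, and includes about 4.6 points after month 24 that no Follow-up 2 page can recover. The recoverable part, about 3.4 points, is below 5.4%.

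**The study is descriptive.** The cohorts are presented separately and no comparison test is planned across risk groups. That limits the consequence, but a descriptive proportion still needs a window that matches its data.

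**Conclusion.** The point holds in this form: the stated scope of the primary endpoints is wider than the scheduled collection of the data that define them. That the regimen page with reasons ends at week 56, and that 7.1.1 and 9.4.4.1 set no window, follows from the text alone. That at least half of the combination cohort is then still on treatment follows from the protocol's expected median, with treatment starting at about baseline. The 53% and the 33-37% rest on an exponential curve.

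The direction is downward if later first events are not captured elsewhere. The size is uncertain: for AE-related termination in the combination cohort, 0 to about 8 points, with about 3.4 before month 24. The documents establish neither a loss for every subject past week 56 nor a bias larger than the planned precision.

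**What to change.** Choose one of two routes.

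1. **Extend collection.** Carry the Visit 2-10 regimen page (dates, dose, and primary reason for change, delay or discontinuation, per drug) to Follow-up 2, covering the interval since Visit 10, and to Follow-up 1 for subjects who stop after Visit 10. State in 7.1.1 and 9.4.4.1 that the window runs to month 24.
2. **Narrow the claim.** If the eCRF is not changed, define and label the primary estimates as through week 56.

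Either way, reconcile 6.1, 7.1.1, 7.2, 9.4.3 and 9.4.4.1. In particular, state whether AEs are collected at Follow-up 2, whether Follow-up 1 is held after a stop beyond Visit 10, and for which subjects reasons for treatment discontinuation can be tabulated. Cumulative incidence of the first AE-related event by week 56 is an optional addition that would put cohorts and risk groups on the same time window.

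Route 1 costs the re-use of one eCRF page and some chart look-back. Enrolment began in Q3 2018 and participation lasts two years, so for some subjects participation has already ended and look-back may be incomplete. Last visits run to Q2 2027, so prospective collection is still possible for later subjects. Route 2 costs only a narrower label.
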